5.5 Use of radiation: N/A

5.6 Use of Center for Magnetic Resonance Research:

Participants will complete three MRI sessions using the 32 channel head coil on a 3T Siemens Prisma scanner (Siemens, Erlangen, Germany) located in the Center for Magnetic Resonance Research (CMRR) at the University of Minnesota. This study will obtain CMRR PARS approval. Structural Imaging and fMRI scanning protocols included in Section 5.2.

5.7 Remote and Limited Study Operations

In the event of research constraints that reduce our capacity for face-to-face contact with subjects, or in cases where MR scanners are not available, we will still carry out as much of the original project as possible. This will be done by completing research procedures using remote data collection and task administration. We will provide subjects with the necessary software and hardware to support remote research procedures.

Remote study operations will proceed according to protocol, with the following differences:

- Study visits that would usually occur in-person will occur via a HIPAA-compliant video connection platform (such as Zoom) or via phone call.
- MRI procedures will not be necessary
- The MATRICS "Spatial Span" task will be dropped due to impracticality of remote administration
- tDCS cognitive training will be self-administered using remote contact with research staff. Training will proceed according to the current protocol, including regular communication with research staff.
- Consent, HIPAA authorization, and UBACC will be collected prior to the baseline visit (see section 20.0 for information on eConsent).
- After the consent, research staff will provide a package(s) to the participant containing the following:
 - 1 Linux appliance with a custom desktop application will be provided to the subject for conducting assessments and training. The custom desktop application running on the Linux appliance does not store any data locally. Collected data is stored on an HST supported server, cnc2.med.umn.edu. The appliance will have the capacity to provide computerized assessment, tDCS training, training tasks, and an integrated HIPAA-compliant video connection platform
 - 1 tDCS stimulation device and headband
 - Sufficient saline vials for the anticipated duration of remote training
 - Sufficient saliva drug screens for the anticipated duration of the study
 - 2 DNA saliva sample kits (if applicable)
 - 1 payment card to be activated and "charged" as appropriate according to the payment schedule
 - Any materials necessary for remote paper-and-pencil assessments (e.g. MATRICS test booklets, pencils, etc.)

PROTOCOL TITLE: Increased thalamocortical connectivity in tDCS-potentiated generalization of cognitive training

VERSION DATE: January 26, 2023

- Other materials as may be needed to complete the protocol, including return labels and packaging as needed for DNA saliva samples, laptop, and tDCS device
- Saliva drug screens and DNA sample kits will be done over Zoom so study staff can verify they are being done correctly by the participant
- All materials will be disinfected before and after shipping

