8.0 Study Population

8.1 Inclusion Criteria:

Cohort 1:

(i) ability to provide consent and comply with study procedures; (ii) age 18 to 60 years old; (iii) estimated IQ range within the specified range ($70 \leq IQ_E \leq 115$); (iv) no Serious and Persistent Mental Illness (SPMI) or addictive disorder diagnosis as measured by the MINI (Mini International Neuropsychiatric Interview; (Sheehan et al., 1998)), or sleep disorder; (v) ability to participate in three weekly 45' training sessions over 12 weeks and participate in four assessments.

Cohort 2:

(i) Ability to provide consent and comply with study procedures; (ii) age 18 to 60 years old; (iii) estimated IQ within the specified range ($70 \leq IQ_E \leq 115$); (iv) schizophrenia or schizoaffective disorder as assessed by the MINI (Mini International Neuropsychiatric Interview)(Sheehan et al., 1998); (v) not having a current addictive disorder as measured by MINI (Mini International Neuropsychiatric Interview), or a sleep disorder; and (vi) ability to participate in the intervention and assessments, as above; (vii) clinically stable and on stable medications for at least one month before start of study.

8.2 Exclusion Criteria:

Exclusion Criteria for Cohort 1 and 2:

(i) any medical condition or treatment with neurological sequelae (e.g. stroke, tumor, loss of consciousness >30 min, concussion involving hospital admission, HIV); (ii) contraindications for tDCS or MRI scanning (tDCS contraindication: history of seizures; MRI contraindications: The research team will utilize the CMRR Center's screening tools and adhere to the screening SOP during enrollment of all research participants in this protocol. The CMRR Center's screening tools and SOP are IRB approved under the CMRR Center Grant (HSC# 1406M51205) and information regarding screening procedures is publicly available on the CMRR website (CMRR Policies / Procedures); (iii) Five or more sessions of neuromodulation (such as tDCS) or cognitive training in the past 12 months

8.3 Screening:

Individuals interested in participating will be screened using a series of questions probing for inclusion and exclusion criteria.

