10.0 Local Number of Participants

10.1 Local Number of Participants to be Consented:

We anticipate screening 300 healthy controls in order to enroll 90 participants in Cohort 1. We anticipate screening 130 SZ Patients in order to enroll 90 participants in Cohort 2.

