The other potential risks pertain to the maintenance of confidentiality. Participants will be probed for personal information during the interviewing process. As noted in the consent form, participants will be told that all diagnostic and other sensitive raw data will be kept in a locked file or secure server and available only to authorized investigators involved in this study. To minimize confidentiality risks, as noted in the consent form, all diagnostic and other sensitive raw data will be kept in a locked file or secure server and be available only to authorized investigators involved in this study. Genetic and epigenetic information will be for research purposes only and will not be included in participants' medical records. Genetic specimens and data will be labeled with the participant's study ID number and will not contain personally identifying information. Participants may opt-in to communication via email by signing a form, "Guidelines and Consent for Unsecured Email Correspondence for Research Participants", notifying them that unsecured emails pose a risk to confidentiality.

MRI risks. Individuals will complete a screening questionnaire for contraindications of MRI scanning. Any affirmative responses on the questionnaire will result in an interview regarding the possible contraindication. An attempt will be made to secure any records of the nature of the possible contraindication and this information will be reviewed by the PI and/or CMRR staff at the University of Minnesota. A determination will be made regarding the level of risk to the subject and whether they are approved for scanning. If approved for scanning by professionals, all risks to the subject will be conveyed to him or her so they can deliberate as to whether or not they want to complete the procedure. Any concerns from the review committee will be conveyed to the participant at that time. If the subject is not approved for scanning, the subject may not have the scan and will be excluded from that part of the study.

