75 completers in cohort 1 and cohort 2 will provide power of .80 to detect effects as small as $\eta^2=.03$ for key confirmatory analyses (tested at $\alpha = .05$) and $\eta^2=.05$ for other analyses (tested at $\alpha=.005$), with nearly as strong power for the analysis of the 24 week follow-up. The more conservative approach of intent-to-treat analysis ($n=90$) will also be conducted for Cohort 2, for which the study will be sensitive to $\eta^2=.027$ (tested at $\alpha = .05$) and $\eta^2=.042$ (tested at $\alpha = .005$). These effect sizes are much smaller than the group x time effect for generalization as measured by the MCCB in our pilot tDCS data ($\eta^2=.08$), suggesting the proposed study is well-powered. While power analyses for neuroimaging studies are challenging due to the interactions of voxelwise-thresholds, brain-wise error correction and spatial smoothness, the proposed studies will be well-powered to detect group x time voxel differences as small as $\eta^2=0.07$ (tested at $\alpha = .001$), and in any case the samples are twice the size of our previous, successfully replicated, neuroimaging studies of brain change following cognitive remediation. Within-group responder analyses conducted for completers ($n=25$ per cell) will have power of .80 to detect correlations $r \geq .34$, a lower magnitude than we already observed ($r=.55$).

15.3 Statistical Analysis:

See section 16.1

15.4 Data Integrity:

The investigator is responsible for ensuring the accuracy, completeness, legibility, and timeliness of the data reported. To enhance scientific rigor, avoid bias and enhance reproducibility, our triple-blind randomized design will use a stratified permuted block randomization procedure (Matts & Lachin, 1988) to roughly equate age and baseline WM performance across groups with a block size of 6. Neither participants nor experimenters will know group assignment. TDCS software programming will allow staff to randomly select one of the three hemisphere conditions (right, left, sham) corresponding to eight letters (six to be distributed evenly among three conditions for HCs, two to be distributed evenly among two conditions for SZs) encoded to preserve the blind. Randomization will be facilitated and the blinding code will be maintained by the study statistician.

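### Section 15.2 states imaging sensitivity with 75 completers per cohort as its only base, while the protocol lets participants complete without MRI; the figure should be restated on scanned completers

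*Combined protocol and SAP*

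**What the plan says.** Section 15.2 opens its power statement with "75 completers in cohort 1 and cohort 2 will provide power of .80 to detect effects as small as" an eta-squared of .03. Later in the same paragraph it says that "the proposed studies will be well-powered to detect group x time voxel differences as small as" eta-squared .07 at alpha .001, and adds that "in any case the samples are twice the size of our previous, successfully replicated, neuroimaging studies of brain change following cognitive remediation". No scanned number is given. For the correlations it refers to "Within-group responder analyses conducted for completers", with 25 per cell, power .80 and r of .34 or more.

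Elsewhere the protocol separates completing from being scanned:

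- Section 5.2 (WM Training with tDCS) defines a complete participant by at least 24 sessions and sets no MRI condition.
- Section 5.2 (Neuroimaging Assessments) limits MRI to those able to attend in person. The footnotes to both schedules of events say that scans may be omitted for safety.
- Section 5.7 says of remote operation that "MRI procedures will not be necessary", while training and most assessments continue.
- Section 13.1 says that if a person is not cleared, "the subject may not have the scan and will be excluded from that part of the study".

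Two sections point the other way. Section 8.2 lists "contraindications for tDCS or MRI scanning" among the exclusions from the trial, and section 5.6 describes three MRI sessions for participants without qualification.

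**The concern.** SA1 is the first aim, and its outcome is thalamocortical functional connectivity (FC). SA3 relates change in FC to generalization and durability. Neither can be tested in a participant without scans, so the sample for both is scanned completers, not completers. If the two numbers differ, the sensitivity in section 15.2 does not describe the analysis it is meant to support. A null imaging result could then be read as evidence against an effect of .07 that the data could not reliably detect.

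Sections 8.2 and 13.1 also disagree on whether MRI ineligibility removes a person from the trial or only from the scan. That leaves the imaging set undefined from the start.

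**Working it through.** **Inputs from the documents.** 75 completers per cohort, power .80, imaging eta-squared .07 at alpha .001, 25 per cell and r of .34 (section 15.2). Cohort 1 has three arms and Cohort 2 has two (section 5.1). Section 4.1 expects Cohort 2 to be smaller than first planned.

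**Inputs not in the documents.** The number of unscanned completers, the number of time points used in the power calculation, and the correlation rho between scans. These are assumed and varied below. Power .80 for the imaging figure is carried over from the start of the paragraph.

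**Formula.** Group by time interaction, noncentral F, with g arms, m time points and N scanned:

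- f² = eta²/(1 − eta²) = .07/.93 = .0753
- lambda = N × f² × m/(1 − rho)
- df1 = (g − 1)(m − 1), df2 = (N − g)(m − 1)

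**Reproducing the plan's figure.** Take g = 3, m = 2, rho = .5, N = 75. Then lambda = 75 × .0753 × 2/.5 = 22.6 on 2 and 72 df, and power is .824. The effect detectable with power .80 is .067, which rounds to .07. The smallest N with power .80 at .07 is 73. Purely between-subject versions give .197 to .224 and do not fit.

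**Fewer scans, same assumptions.** At N = 72, lambda = 21.7 and power is .797. At N = 60 (20% unscanned), lambda = 18.1 and power is .66, with detectable effect .085. At N = 45 (40% unscanned), lambda = 13.5 and power is .43, with detectable effect .115.

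**Range over the unstated inputs** (power at eta-squared .07, alpha .001):

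| Arms | Time points | rho | 75 scanned | 60 | 45 | Detectable at 75 |
|---|---|---|---|---|---|---|
| 3 | 2 | .5 | .82 | .66 | .43 | .067 |
| 3 | 3 | .5 | .95 | .85 | .63 | .052 |
| 3 | 3 | .3 | .79 | .61 | .38 | .071 |
| 2 | 2 | .5 | .90 | .78 | .56 | .058 |
| 2 | 3 | .5 | .98 | .93 | .77 | .044 |
| 2 | 3 | .3 | .89 | .75 | .53 | .060 |

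The two three-arm rows whose detectable effect rounds to .07 leave almost no room. One needs 73 scanned, and the other is already just under .80 at 75. With three time points and rho .5, three-arm power stays at .80 or more down to 56 scanned. With two arms, two time points and rho .5, it does so down to 63, so 12 of 75 could go unscanned.

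**SA3 correlation.** By Fisher's z, the smallest r detectable with power .80 is tanh[(z_alpha + z_power)/√(n − 3)]. With n = 25:

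- two-sided alpha .05: tanh(2.80/4.69) = .54
- one-sided alpha .05: tanh(2.49/4.69) = .49

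Power at r = .34 is .38 two-sided or .51 one-sided; a simulation gave .39 and .52. Reaching .80 at r = .34 needs about 66 (two-sided) or 53 (one-sided). Two arms in Cohort 2 would put 37 or 38 in each cell if 75 completed; the detectable r is then about .44 to .45 two-sided or .40 one-sided, still above .34. All of this assumes every completer is scanned.

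**The case against.** The strongest reply is that no loss has been shown. Remote operation in section 5.7 is a contingency, section 5.6 still describes three scans, and MRI eligibility is asked before enrolment, so scan-only exclusion may be rare. The documents give no unscanned number, and the 20% and 40% used above are illustrations. Section 15.2 attaches no N to the imaging sentence and itself warns that imaging power is hard to calculate. Section 15.1 examines group by time over three points, and with three time points and rho .5 a 20% loss still leaves .85. All of this stands. A reader might infer that the trial cannot deliver its imaging sensitivity, or that two time points and rho .5 are the plan's own method. The documents support neither.

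The comparison with earlier imaging studies also tolerates some loss: twice the larger one in section 2.2 (15 + 12 = 27) is 54. But that is a comparison of sizes, not a detectable effect.

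A reader might also blame missing scans for the SA3 shortfall. That does not follow, because r of .34 fails at 25 per cell with every scan in hand. Missing scans only make it worse.

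Finally, one scanned number does not serve every hypothesis. H2.3 relates modeled dosage to cognitive outcomes. If the individual field model is built from anatomy, as section 2.3 implies, a baseline structural scan would be enough.

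What the reply does not remove is the mismatch itself: several sections allow completion without MRI, and section 15.2 makes no allowance for it.

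**Conclusion.** The concern holds as a conditional one. Section 15.2 states its imaging sensitivity with no completer base other than 75 per cohort, and the protocol lets that base shrink for the analyses that need scans. That the figure refers to 75 scanned completers is inferred from the paragraph, though the reproduction supports it.

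Under the three-arm assumptions that reproduce .07, the claim needs nearly all completers scanned: three unscanned out of 75 bring power just under .80. More favourable inputs leave real slack, and so does a two-arm Cohort 2 if it still reaches 75. Whether the sensitivity is met cannot be settled without the scanned number, the time points and rho. The r of .34 at 25 per cell is a separate error that rests on neither missing scans nor rho. The conflicts between sections 8.2 and 13.1, and between 5.6 and 5.7, need no assumption.

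**What to change.** - Restate section 15.2 for SA1 and SA3 on the expected or actual number of scanned completers per arm in each cohort, using two arms and the reduced size for Cohort 2. State the time points and between-scan correlation assumed, and give a range if they are uncertain.
- For H2.3, use the number with a baseline structural scan.
- Define the imaging analysis set and say how missing scans are handled.
- Correct the within-group correlation statement: about .54 two-sided or .49 one-sided at 25 per cell, or whatever the scanned number per cell supports.
- Reconcile section 8.2 with 13.1 on whether MRI ineligibility excludes from the trial or only from the scan, and section 5.6 with 5.7 on whether scans are required.

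The cost is a less favourable stated sensitivity and some wording changes. No patients are added.

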6.0 Data and Specimen Banking

6.1 Storage and Access:

Data collected for this study will be maintained and stored in REDCap, Box and AHC-IS password protected servers.

Only research staff will have access to subject information. Records containing identifying information will be stored in a private research office in a locked file cabinet or on a secure server and will be accessible only by the principal investigator and study staff. The passwords for accessing this information will be available to only select staff that need access to the information to conduct their research duties.

All biological specimens for genetic analyses collected through this protocol will be stored in the laboratory of [name] at the University of Minnesota ([name]). All specimens will be labeled and stored with a study specimen number, not with any personal or protected health information.

6.2 Data: List all of the data elements to be collected and banked for future use.

Data will be uploaded to the National Institute of Mental Health Data Archive (NDA) (see section 6.3 below).

Genetic data may be banked for future studies. Participants will choose on the consent form whether or not they wish for their specimens to be banked for future studies.

6.3 Release/Sharing:

The data collected may represent a unique resource for some investigators. We will make the de-identified data available to interested investigators who contact us for access to the data. As the proposed work is a clinical trial, the most appropriate database for our collected data appears to be clinicaltrials.gov. The investigator, co-investigator, and research staff will permit trial-related monitoring, audits, IRB/IEC(s) review and regulatory inspection(s) by providing direct access to source data/documentation.

Data will also be uploaded to the National Institute of Mental Health Data Archive (NDA), a repository run by the National Institute of Mental Health (NIMH) that allows researchers studying mental illness to collect and share information with each other. All personal information about research participants such as name, address, and phone number will be removed from these data and replaced with a code number before uploading to NDA. Research participants will be informed about NDA data sharing in the consent process and notified that they may choose to not participate in the study if they do not wish for their data to be shared with NDA.

7.0 Sharing of Results with Participants

PROTOCOL TITLE: Increased thalamocortical connectivity in tDCS-potentiated generalization of cognitive

training

VERSION DATE: January 26, 2023

7.1 Individual and group results, including results from genetic analyses, will not be directly shared with research participants. Participants will be informed that they can learn more about the outcome of this study upon completion at clinicaltrials.gov or on the investigators' personal laboratory research.

8.0 Study Population

8.1 Inclusion Criteria:

Cohort 1:

(i) ability to provide consent and comply with study procedures; (ii) age 18 to 60 years old; (iii) estimated IQ range within the specified range ($70 \leq IQ_E \leq 115$); (iv) no Serious and Persistent Mental Illness (SPMI) or addictive disorder diagnosis as measured by the MINI (Mini International Neuropsychiatric Interview; (Sheehan et al., 1998)), or sleep disorder; (v) ability to participate in three weekly 45' training sessions over 12 weeks and participate in four assessments.

Cohort 2:

(i) Ability to provide consent and comply with study procedures; (ii) age 18 to 60 years old; (iii) estimated IQ within the specified range ($70 \leq IQ_E \leq 115$); (iv) schizophrenia or schizoaffective disorder as assessed by the MINI (Mini International Neuropsychiatric Interview)(Sheehan et al., 1998); (v) not having a current addictive disorder as measured by MINI (Mini International Neuropsychiatric Interview), or a sleep disorder; and (vi) ability to participate in the intervention and assessments, as above; (vii) clinically stable and on stable medications for at least one month before start of study.

8.2 Exclusion Criteria:

Exclusion Criteria for Cohort 1 and 2:

(i) any medical condition or treatment with neurological sequelae (e.g. stroke, tumor, loss of consciousness >30 min, concussion involving hospital admission, HIV); (ii) contraindications for tDCS or MRI scanning (tDCS contraindication: history of seizures; MRI contraindications: The research team will utilize the CMRR Center's screening tools and adhere to the screening SOP during enrollment of all research participants in this protocol. The CMRR Center's screening tools and SOP are IRB approved under the CMRR Center Grant (HSC# 1406M51205) and information regarding screening procedures is publicly available on the CMRR website (CMRR Policies / Procedures); (iii) Five or more sessions of neuromodulation (such as tDCS) or cognitive training in the past 12 months

8.3 Screening:

Individuals interested in participating will be screened using a series of questions probing for inclusion and exclusion criteria.

Cohort 1: Study staff or weblinks will direct interested individuals to a HIPAA compliant online portal with a thorough description of the requirements of the study. At this time, interested individuals will answer relevant screening questions, including tDCS or MRI contraindications. If a volunteer appears eligible based on their answers to the online screening questions, study staff will call the volunteer on the phone to answer additional screening questions and to complete items from a neuropsychological vocabulary test. Alternatively, Cohort 1 volunteers can complete the entire screening process over the phone if needed. If the HC volunteer fulfills inclusion and exclusion criteria, they will be invited to participate and scheduled for the pretest assessment.

Cohort 2: Through a voice call or in-person meeting study staff will ask potential participants in Cohort 2 screening questions about demographics, likely diagnosis, MRI eligibility and cognitive ability. Alternatively, potential participants may complete elements of the prescreening process through the HIPAA-compliant online

PROTOCOL TITLE: Increased thalamocortical connectivity in tDCS-potentiated generalization of cognitive

training

VERSION DATE: January 26, 2023

portal described above. Volunteers will also complete items from a neuropsychological vocabulary test. Research staff will then inquire about the participant's transportation needs and offer assistance as needed to attend any in-person study appointments. If the SZ volunteer fulfills inclusion and exclusion criteria below, they will be invited to participate and scheduled for a pretest assessment.

Vocabulary test and IQ ranges: The purpose of the neuropsychological vocabulary test is to screen out individuals in both cohorts who are likely to fall outside the desired IQ range of $70 < IQ_E \leq 115$. Importantly, scores on the vocabulary test do not represent actual IQ *per se*, but will be used to efficiently estimate a range within which a volunteer's IQ is likely to fall.

- Cohort 1 (HC): because the mean IQ of the university community is approximately 115, we will use an estimated IQ (IQ_E) range $70 < IQ_E \leq 115$ for inclusion. This screening will substantially reduce the number of eligible participants, and is accounted for in our recruitment strategy.
- Cohort 2 (SZ): our goal is to study the portion of the SZ population that is most cognitively impaired and may therefore gain significantly from generalization of cognitive training, however we will also wish to rule-out cognitive disabilities. SZ mean performance on cognitive batteries is approximately 1 SD below the mean (85 IQ)(Dickinson, Ramsey, & Gold, 2007). We will use the estimated IQ range $70 < IQ_E \leq 115$ as appropriate for inclusion. We anticipate that this screening will not substantially reduce the number of eligible SZ participants as this is a large proportion of the population.

If potential participants in both cohorts meet the pre-screening criteria, they will be invited to participate and scheduled for a screening visit, where they will review and sign a consent prior to completing the screening assessment, which includes the MINI. The MINI will be administered in order to rule out current Serious and Persistent Mental Illness (SMPI) and addictive disorders for Cohort 1, and to confirm diagnosis and rule out current addictive disorders for Cohort 2.

